APPENDIX 4 WOMEN OF CHILDBEARING POTENTIAL DEFINITIONS AND METHODS OF CONTRACEPTION

Appendix 4 provides general information and definitions related to WOCBP and methods of contraception that can be applied to most clinical trials. For information specific to this study regarding acceptable contraception requirements for female participants, refer to [Section 6.1](#) of the protocol. Only the contraception methods described in Section 6.1 are acceptable for this study.

DEFINITIONS

Woman of Childbearing Potential

A woman is considered fertile following menarche and until becoming postmenopausal unless permanently sterile. Permanent sterilization methods include hysterectomy, bilateral salpingectomy, and bilateral oophorectomy.

Women in the following categories are not considered WOCBP:

- Premenarchal
- Pre-menopausal female with one of the following:
 - Documented hysterectomy
 - Documented bilateral salpingectomy
 - Documented bilateral oophorectomy
- Post-menopausal female
 - A post-menopausal state is defined as 12 months of amenorrhea in a woman over the age of 45 years in the absence of other biological or physiological causes. In addition, females under the age of 55 years must have a serum follicle-stimulating hormone (FSH) level > 40 mIU/mL to confirm menopause.

Note: Documentation can come from the site personnel's review of the participant's medical records, medical examination, or medical history interview.

- 1-week minimum for vaginal hormonal products (rings, creams, gels)
- 4-week minimum for transdermal products
- 8-week minimum for oral products

Other parenteral products may require washout periods as long as 6 months. If the serum FSH level is > 40 mIU/mL at any time during the washout period, the woman can be considered postmenopausal.

End of Relevant Systemic Exposure

End of relevant systemic exposure is the time point at which the study intervention (IMP and other study interventions, ie, non-IMP/auxiliary medicinal product required for study) or any active major metabolites have decreased to a concentration that is no longer considered relevant for human teratogenicity or fetotoxicity. This should be evaluated in the context of safety margins from the no-observed-adverse-effect level or the time required for 5 half-lives of the study intervention to pass.

METHODS OF CONTRACEPTION

Local laws and regulations may require use of alternative and/or additional contraception methods.

Highly Effective Contraceptive Methods That Are User Dependent

Failure rate of < 1% per year when used consistently and correctly.^a

- Combined (estrogen- and progestogen-containing) hormonal contraception associated with inhibition of ovulation and/or implantation. (This method of contraception can only be used by WOCBP participants in studies in which hormonal contraception is permitted by the study protocol.)^b
 - Oral (birth control pills)
 - Intravaginal (rings)
 - Transdermal
- Combined (estrogen- and progestogen-containing) hormonal contraception must begin at least 30 days prior to initiation of study intervention.
- Progestogen-only hormonal contraception associated with inhibition of ovulation. (This method of contraception can only be used by WOCBP participants in studies in which hormonal contraception is permitted by the study protocol.)^b
 - Oral
 - Injectable
- Progestogen-only hormonal contraception must begin at least 30 days prior to initiation of study intervention.

Highly Effective Methods That Are User Independent

- Implantable progestogen-only hormonal contraception associated with inhibition of ovulation and/or implantation. (This method of contraception can only be used by WOCBP participants in studies in which hormonal contraception is permitted by the study protocol.)^b
- Intrauterine device.
- Intrauterine system (IUS). (This method of contraception can only be used by WOCBP participants in studies in which hormonal contraception is permitted by the study protocol.)^{b,c}
- Bilateral tubal occlusion.

- Vasectomized partner.

Having a vasectomized partner is a highly effective contraception method provided that the partner is the sole male sexual partner of the WOCBP and the absence of sperm has been confirmed. If not, an additional highly effective method of contraception should be used.

- Sexual abstinence.

Sexual abstinence is considered a highly effective method only if defined as refraining from heterosexual intercourse during the entire period of risk associated with the study intervention. The reliability of sexual abstinence needs to be evaluated in relation to the duration of the study and the preferred and usual lifestyle of the participant.

- Continuous abstinence must begin at least 30 days prior to initiation of study intervention.
- It is not necessary to use any other method of contraception when complete abstinence is elected.
- WOCBP participants who choose complete abstinence must continue to have pregnancy tests, as specified in [Section 2](#) of the protocol.
- Acceptable alternate methods of highly effective contraception must be discussed in the event that the WOCBP participant chooses to forego complete abstinence.
- Periodic abstinence (including, but not limited to, calendar, symptothermal, post-ovulation methods), withdrawal (coitus interruptus), spermicides only, and lactation amenorrhea method (LAM) are not acceptable methods of contraception for this study.

NOTES:

- ^a Typical use failure rates may differ from failure rates when contraceptive methods are used consistently and correctly. Use should be consistent with local regulations regarding the use of contraceptive methods for participants in clinical studies.
- ^b Hormonal contraception may be susceptible to interaction with the study intervention, which may reduce the efficacy of the contraceptive method. Hormonal contraception is permissible only when there is sufficient evidence that the IMP and other study medications will not alter hormonal exposures such that contraception would be ineffective or result in increased exposures that could be potentially hazardous. In this case, alternative methods of contraception should be utilized. For information specific to this study regarding permissibility of hormonal contraception, refer to [Sections 6.1](#) Inclusion Criteria and [7.7.1](#) Prohibited and/or Restricted Treatments of the protocol.
- ^c IUS are acceptable methods of contraception in the absence of definitive drug interaction studies when hormone exposures from intrauterine devices do not alter contraception effectiveness. For information specific to this study regarding permissibility of hormonal contraception, refer to [Sections 6.1](#) Inclusion Criteria and [7.7.1](#) Prohibited and/or Restricted Treatments of the protocol.

Less Than Highly Effective Contraceptive Methods That Are User Dependent

Failure rate of > 1% per year when used consistently and correctly.

- Male or female condom with or without spermicide. Male and female condoms cannot be used simultaneously.
- Diaphragm with spermicide.

- Cervical cap with spermicide.
- Vaginal sponge with spermicide.
- Progestogen-only oral hormonal contraception, where inhibition of ovulation is not the primary mechanism of action. (This method of contraception cannot be used by WOCBP participants in studies in which hormonal contraception is prohibited.)

Unacceptable Methods of Contraception

- Periodic abstinence (calendar, symptothermal, post-ovulation methods)
- Withdrawal (coitus interruptus)
- Spermicide only
- LAM

COLLECTION OF PREGNANCY INFORMATION

Guidance for collection of pregnancy information and outcome of pregnancy on the Pregnancy Surveillance Form is provided in [Section 9.2.5: Pregnancy](#) of the protocol and [APPENDIX 4](#).

APPENDIX 5 ADVERSE EVENTS AND SERIOUS ADVERSE EVENTS: DEFINITIONS AND PROCEDURES FOR RECORDING, EVALUATING, FOLLOW-UP, AND REPORTING

ADVERSE EVENTS

AE Definition
An AE is defined as any new untoward medical occurrence or worsening of a pre-existing medical condition occurring in a clinical investigation participant after signing of informed consent, whether or not considered related to the study intervention.
An AE can therefore be any unfavorable and unintended sign (such as an abnormal laboratory test result), symptom, or disease temporally associated with the study intervention.
Events Meeting the AE Definition

Any abnormal laboratory test results (hematology, clinical chemistry, or urinalysis) or results from other safety assessments (eg, ECGs, radiological scans, vital sign measurements), including those that worsen from baseline, considered clinically significant in the medical and scientific judgment of the investigator. Note that abnormal laboratory test results or other safety assessment findings should only be reported as AEs if the final diagnosis is not available. Once the final diagnosis is known, the reported term should be updated to be the diagnosis.Exacerbation of a chronic or intermittent pre-existing condition, including either an increase in frequency and/or intensity of the condition.New conditions detected or diagnosed after study intervention administration, even though the condition may have been present before the start of the study.Signs, symptoms, or the clinical sequelae of a suspected drug-drug interaction.Signs, symptoms, or the clinical sequelae of a suspected overdose of either study intervention or a concomitant medication. Overdose, as a verbatim term (as reported by the investigator), should not be reported as an AE/SAE unless it is an intentional overdose taken with possible suicidal/self-harming intent. Such overdoses should be reported regardless of sequelae and should specify “intentional overdose” as the verbatim term.
Events NOT Meeting the AE Definition

Medical or surgical procedure (eg, endoscopy, appendectomy); the condition that leads to the procedure is the AE.Situations in which an untoward medical occurrence did not occur (social and/or convenience admission to a hospital).

DEFINITION OF SAE

If an event is not an AE per the definition above, then it cannot be an SAE, even if serious conditions are met.

SERIOUS ADVERSE EVENTS

A SAE is defined as any untoward medical occurrence that, at any dose:
Results in death.
Is life-threatening (defined as an event in which the participant was at risk of death at the time of the event; it does not refer to an event that hypothetically might have caused death if it were more severe).
Requires inpatient hospitalization or causes prolongation of existing hospitalization (see NOTE below).
NOTE: The following hospitalizations are not considered SAEs in BMS clinical studies:

• A visit to the emergency department or other hospital department < 24 hours that does not result in admission (unless considered an important medical or life-threatening event).• Elective surgery that was planned prior to signing consent.• Admissions per protocol for a planned medical/surgical procedure.• Routine health assessment requiring admission for baseline/trending of health status (eg, routine colonoscopy).• Medical/surgical admission other than to remedy ill health and planned prior to enrollment in the study. Appropriate documentation is required in these cases.• Admission encountered for another life circumstance that carries no bearing on health status and requires no medical/surgical intervention (eg, lack of housing, economic inadequacy, caregiver respite, family circumstances, administrative reason).• Admission for administration of anticancer therapy in the absence of any other SAEs (applies to oncology protocols).
Results in persistent or significant disability/incapacity.
Is a congenital anomaly/birth defect.
Is an important medical event (defined as a medical event[s] that may not be immediately life-threatening or results in death or hospitalization but, based upon appropriate medical and scientific judgment, may jeopardize the participant or may require intervention [eg, medical, surgical] to prevent one of the other serious outcomes listed in the definition above). Examples of such events include, but are not limited to, intensive treatment in an emergency department or at home for allergic bronchospasm and blood dyscrasias or convulsions that do not result in hospitalization. Potential DILI is also considered an important medical event. (See Section 9.2.7 : Potential DILI of the protocol for the definition of a potential DILI.)

Pregnancy and DILI must follow the same transmission timing and processes to BMS as those used for SAEs. (See [Section 9.2.5](#): Pregnancy of the protocol for reporting pregnancies.)

EVALUATING AES AND SAES

Assessment of Causality

- The investigator is obligated to assess the relationship between study intervention and each occurrence of each AE/SAE.
- A “reasonable possibility” of a relationship conveys that there are facts, evidence, and/or arguments to suggest a causal relationship, rather than a relationship cannot be ruled out.
- The investigator will use clinical judgment to determine the relationship.
- Alternative causes, such as underlying disease(s), concomitant therapy, and other risk factors, as well as the temporal relationship of the event to study intervention administration, will be considered and investigated.
- The investigator will also consult the product information for marketed products, in his/her assessment.
- For each AE/SAE, the investigator must document in the medical notes that he/she has reviewed the AE/SAE and has provided an assessment of causality.
- There may be situations in which an SAE has occurred and the investigator has minimal information to include in the initial report to the Sponsor. However, it is very important that the investigator always make an assessment of causality for every event before the initial transmission of the SAE data to the Sponsor.
- The investigator may change his/her opinion of causality in light of follow-up information and send an SAE follow-up report with the updated causality assessment.
- The causality assessment is one of the criteria used when determining regulatory reporting requirements.

• Assessment of Intensity

The investigator will make an assessment of intensity for each AE and SAE reported during the study and assign it to one of the following categories:

- Mild: An event that is easily tolerated by the participant, causing minimal discomfort and not interfering with everyday activities.
- Moderate: An event that causes sufficient discomfort and interferes with normal everyday activities.
- Severe: An event that prevents normal everyday activities. An AE that is assessed as severe should not be confused with an SAE. Severe is a category utilized for rating the intensity of an event, and both AEs and SAEs can be assessed as severe.

An event is defined as “serious” when it meets at least one of the pre-defined outcomes as described in the definition of an SAE, NOT when it is rated as severe.

Follow-up of AEs and SAEs

If only limited information is initially available, follow-up reports are required. (Note: Follow-up SAE reports must include the same investigator term[s] initially reported.)

If an ongoing SAE changes in its intensity or relationship to study intervention or if new information becomes available, the SAE report must be updated and submitted within 24 hours to BMS (or the designee) using the same procedure used for transmitting the initial SAE report.

All AEs/SAEs must be followed to resolution or stabilization.

REPORTING OF SAEs TO SPONSOR OR DESIGNEE

- SAEs, whether related or not related to study intervention, and pregnancies must be reported to BMS (or the designee) promptly and not to exceed 24 hours of awareness of the event.
- SAEs must be recorded on the SAE Report Form.
 - The required method for SAE data reporting is through the eCRF.
 - The paper SAE Report Form is intended only as a back-up option when the EDC system is unavailable/not functioning for transmission of the eCRF to BMS (or the designee).
 - ◆ In this case, the paper form is transmitted via email or confirmed fax transmission.
 - ◆ When paper forms are used, the original paper forms are to remain on site.
- Pregnancies must be recorded on paper Pregnancy Surveillance Forms and transmitted via email or confirmed fax transmission.

SAE Email Address: SAE reporting contact information will be provided locally

SAE Fax Number: SAE reporting contact information will be provided locally.

SAE Telephone Contact (required for SAE and pregnancy reporting): SAE reporting contact information will be provided locally.

APPENDIX 6 SELECTED ENDPOINT DEFINITIONS

Clinical Response (modified Mayo score, primary endpoint)	Achieving the following changes from baseline in the modified Mayo score: 
• A decrease from baseline in the modified Mayo score ≥ 2 points, and• A decrease from baseline in the modified Mayo score $\geq 35\%$, and• A decrease from baseline in RB subscore ≥ 1 point or absolute RB subscore ≤ 1.
Clinical Remission (modified Mayo score)	A modified Mayo score with the following: 
• SF subscore ≤ 1, with ≥ 1 point decrease from baseline, and• RB subscore = 0, and• ES ≤ 1
Clinical Remission (partial Mayo)	Partial Mayo score ≤ 2.5
Endoscopic Response	A decrease from baseline of ≥ 1 point in Mayo ES
Endoscopic Improvement	Mayo ES ≤ 1

Endoscopic Remission		Mayo ES = 0
Histological Improvement	•	• Achieving a Geboes score < 3.1
Histologic Remission		Achieving Geboes score < 2
HEMI		Mayo ES \leq 1 and a Geboes score < 3.1
Corticosteroid-free Clinical Remission (modified Mayo score)		Clinical remission (by modified Mayo criteria), and no oral systemic steroid use in prior 90 days.
Corticosteroid-free Clinical Remission (partial Mayo score)		Clinical remission (by partial Mayo criteria), and no oral systemic steroid use in prior 90 days.

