Secondary 
To explore the efficacy of ozanimod in the advanced therapy-exposed cohort.	Secondary 
Clinical remission at Week 26, as measured by modified Mayo score.Endoscopic response at Week 26.Endoscopic improvement at Week 26.Endoscopic remission at Week 26.Histological improvement at Week 26.Histological remission at Week 26.Change in the IBDQ total score from baseline to Week 26.IBDQ response (change in total score [\geq 16 points] from baseline to Week 26).IBDQ remission (total score [\geq 170 points]) at Week 26.Corticosteroid-free clinical remission at Week 26, as measured by modified Mayo score.HEMI at Week 26.

HEMI, histo-endoscopic mucosal improvement; IBDQ, Inflammatory Bowel Disease Questionnaire.

Table 4-3: Additional Objectives and Endpoints Common for both the Advanced Therapy-naïve Cohort (Cohort 1) and the Advanced Therapy-exposed Cohort (Cohort 2) after Week 26

Objectives	Endpoints

Secondary
 
• To explore the safety and tolerability of ozanimod in the advanced therapy-naïve cohort and the advanced therapy-exposed cohort.• To explore the long-term durability of response to ozanimod in the advanced therapy-naïve cohort and the advanced therapy-exposed cohort.	
Secondary
 
• Number and proportion of participants experiencing the following:
– AEs.– SAEs.– AEs and SAEs, including AEIs and other select AEs, leading to discontinuation from the study intervention and the study.– Clinical laboratory values.• Clinical remission by partial Mayo score at Weeks 52 and 104.• Corticosteroid-free clinical remission by partial Mayo score at Weeks 52 and 104.• Clinical response by partial Mayo score at Weeks 52 and 104.

Table 4-3: Additional Objectives and Endpoints Common for both the Advanced Therapy-naïve Cohort (Cohort 1) and the Advanced Therapy-exposed Cohort (Cohort 2) after Week 26

Objectives	Endpoints
AEI, adverse event of interest;	SAE, serious adverse event;

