6.1 Inclusion Criteria

Participants are eligible to be included in the study only if all of the following criteria apply:

1) Signed Written Informed Consent

- a) Participants must have signed and dated an Institutional Review Board (IRB)/Independent Ethics Committee (IEC)-approved written informed consent form (ICF) in accordance with regulatory, local, and institutional guidelines. This must be obtained before the performance of any protocol-related procedures that are not part of normal patient care.

2) Type of Participant and Target Disease Characteristics

- a) A diagnosis of UC, with signs and symptoms consistent with UC for at least 3 months prior to the first study intervention administration.
- b) Moderate to severely active UC disease activity, defined as a modified Mayo score of 4 through 9, inclusive, with the following minimum subscores:
 - i) An SF subscore ≥ 1 ,

AND

ii) An RB subscore ≥ 1 ,

AND

iii) An ES ≥ 2 (endoscopy performed within 60 days of the first study intervention administration).

- c) Must be up to date with screening for colorectal neoplasia and surveillance for dysplasia, according to local standard of care.
- d) Must have documentation of positive VZV IgG antibody status at screening or complete VZV vaccination prior to the first study intervention administration.
- e) Report of a previous colonoscopy that documents extent of disease (Note: If performed in the prior 60 days, this data may be used for study inclusion.)
- f) UC disease distribution (including ulcerative proctitis) extending proximal to the rectum (ie, approximately ≥ 5 cm from anal margin).

3) Age of Participant

- a) Participant must be over 18 years of age (or the legal age of consent in the jurisdiction in which the study is taking place) at the time of signing the informed consent.

4) Cohort 1 (Advanced Therapy-naïve Cohort): Disease Distribution and Prior UC Medication Exposure

In order to participate in Cohort 1, a participant must meet the eligibility criteria outlined in this inclusion criterion (IC) and must not meet the eligibility criteria outlined in IC 5.

- a) Participants must be naïve to 6-mercaptopurine/AZA and any biologics (see IC 5[a] for list) for any other medical indication, as well as UC.

5) Cohort 2 (Advanced Therapy-exposed Cohort): Disease Distribution and Prior UC Medication Exposure

In order to participate in Cohort 2, a participant must have failed only one mechanism of action of biologics.

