10.4.3 Primary Endpoint

The primary endpoint for each cohort, their corresponding descriptions, and prespecified time points are listed in Table 10.4.3-1.

The primary endpoint for Cohort 1 is the proportion of participants who achieve a clinical response at Week 12. The clinical response rate at Week 12 will be estimated, and the corresponding 95% CI will be derived based on the Clopper Pearson method.

The primary endpoint for Cohort 2 is the proportion of participants who achieve a clinical response at Week 26. An estimate of the clinical response rate at Week 26 will be provided, along with the corresponding 95% CI derived based on the Clopper Pearson method.

For proportion-based efficacy endpoints, patients with missing Week 12 efficacy data from Cohort 1 and/or participants with missing Week 26 efficacy data from Cohort 2 will be considered non-responders, and non-responder imputation will be used. Sensitivity analyses around missing data may involve missing data imputed using multiple imputation and may analyze observed cases with no imputation. Details of the sensitivity analysis will be provided in the SAP.

For continuous efficacy endpoints, observed cases will be analyzed with no imputation.

Table 10.4.3-1: Endpoints

Primary	Description	Timeframe
Clinical Response (modified Mayo score)	Proportion of participants achieving the following: 
Decrease from baseline in the modified Mayo score of ≥ 2 points, andDecrease from baseline in the modified Mayo score of $\geq 35\%$, andDecrease in RB subscore of ≥ 1 point or absolute RB subscore ≤ 1.	Week 12 (Cohort 1) Week 26 (Cohort 2)
Secondary	Description	Timeframe
Clinical Remission (modified Mayo score)	Proportion of treated participants achieving the following in each component of the modified Mayo score: 
SF subscore ≤ 1, with ≥ 1-point decrease from baseline, andRB subscore = 0, andES ≤ 1.	Week 12 (Cohort 1) Week 26 (Cohort 2)
Endoscopic Response	Proportion of treated participants with a decrease from baseline of ≥ 1 point in Mayo ES	Week 12 (Cohort 1) Week 26 (Cohort 2)
Endoscopic Improvement	Proportion of treated participants with Mayo ES ≤ 1	Week 12 (Cohort 1) Week 26 (Cohort 2)

Table 10.4.3-1: Endpoints

Endoscopic Remission	Proportion of treated participants with Mayo ES = 0	Week 26 (Cohort 2)
IBDQ Response	Proportion of participants with a change from baseline in total score of ≥ 16 points	Week 12 (Cohort 1)

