- 4) Agreement to be accountable for all aspects of the work in ensuring that questions related to the accuracy or integrity of any part of the work are appropriately investigated and resolved.

Those who make the most significant contributions, as defined above, will be considered by the Sponsor for authorship of the primary publication. Sub-investigators will generally not be considered for authorship in the primary publication. Geographic representation will also be considered.

Authors will be listed by order of significant contributions (highest to lowest), with the exception of the last author. Authors in first and last position have provided the most significant contributions to the work.

For secondary analyses and related publications, author list and author order may vary from primary to reflect additional contributions.

Participants must be informed that their study-related data (including but not limited to), such as endoscopy images, may be used for the publication of results, if required.

**APPENDIX 3 SELECTED INSTRUMENT DEFINITIONS (BASED ON
PERMUTATIONS OF THE MAYO SCORE)**

Modified Mayo Score	Sum of the following components of the Mayo score (Range 0-9): 
• SF subscore: Range 0-3• RB subscore: Range 0-3• ES: Range 0-3 ES is modified from the original description: Friability is not included in ES = 1.
Partial Mayo Score	Sum of the following components of the Mayo score (Range 0-9): 
• SF subscore: Range 0-3• RB subscore: Range 0-3• PGA: Range 0-3

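### Partial Mayo remission at Weeks 52 and 104 has no subscore condition, so it can be met with rectal bleeding still present and, for participants who enter at SF 1 and RB 1, with both symptoms unchanged

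*Combined protocol and SAP*

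**What the plan says.** Table 4-3 lists "Clinical remission by partial Mayo score at Weeks 52 and 104" as a secondary endpoint for both cohorts, under the objective on long-term durability of response. Appendix 6 defines it in full as "Partial Mayo score ≤ 2.5". The corticosteroid-free version takes over the same rule: "Clinical remission (by partial Mayo criteria), and no oral systemic steroid use in prior 90 days". Appendix 3 builds the partial Mayo score from SF, RB and PGA, each scored 0 to 3.

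Entry criterion 2b in Section 6.1 describes active disease as "defined as a modified Mayo score of 4 through 9, inclusive, with the following minimum subscores". Two of those minimums are "An SF subscore ≥ 1" and "An RB subscore ≥ 1", and the third is an endoscopic subscore (ES) of at least 2. There is no minimum PGA.

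Remission at Week 12 (Cohort 1) and Week 26 (Cohort 2) uses the modified Mayo score instead. Table 10.4.3-1 requires "SF subscore ≤ 1, with ≥ 1-point decrease from baseline", together with an RB subscore of 0 and an ES of at most 1.

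Section 5.1 describes the PGA as physician-reported, and Section 7.3 states that site personnel are not blinded. Tables 2-1 and 2-2 schedule no endoscopy at Week 52 or Week 104.

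**The concern.** The long-term rule limits a total and nothing else. It does not ask for bleeding to have stopped, for stool frequency to be near normal, or for any fall from baseline. Criterion 2b admits participants whose two symptom scores sum to only 2, so for them the total can be met without symptom change. One of the three components is a rating by a physician who knows the treatment, and no endoscopic finding is available at those visits to set against it.

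The study has no control group and tests no hypothesis, so the reported percentage is the whole result for this endpoint. The same word, remission, is used at Weeks 12 and 26 under a stricter symptom rule. A reader who sets the two rates side by side as evidence of durability would be comparing different definitions.

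**Working it through.** **Inputs.** SF, RB and PGA each 0 to 3 (Appendix 3). Remission if SF + RB + PGA ≤ 2.5 (Appendix 6). Entry: SF ≥ 1, RB ≥ 1, ES ≥ 2, modified Mayo score 4 to 9 (Section 6.1). Integer subscores are assumed unless stated otherwise.

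**1. The plan's own entry limit.** Minimum modified Mayo score = SF 1 + RB 1 + ES 2 = 4, which agrees with the stated lower limit. Under these minimums, SF 1, RB 1, ES 2 is the only way to score 4.

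**2. Remission with both symptoms unchanged.** With SF and RB fixed at entry values, the lowest possible score is SF + RB + 0. There are 3 × 3 = 9 eligible SF/RB pairs.

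- Pair (1,1): 1 + 1 + 0 = 2 ≤ 2.5, so remission is possible.
- Each of the other 8 pairs: SF + RB ≥ 3 > 2.5, so no PGA value gives remission unless symptoms improve.

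For the (1,1) pair:

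| Baseline PGA | Baseline score | Rule met at baseline? | Score if only PGA moves to 0 |
|---|---|---|---|
| 0 | 2 | Yes | 2 (no change needed) |
| 1 | 3 | No | 2, remission |
| 2 | 4 | No | 2, remission |
| 3 | 5 | No | 2, remission |

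**3. Remission with continuing bleeding.** Ten (SF, RB, PGA) combinations sum to 2 or less. Four have RB ≥ 1: (0,1,0), (0,1,1), (0,2,0) and (1,1,0). The first three require SF to fall to 0 from an entry value of at least 1. In (0,2,0), bleeding is unchanged for someone who entered at RB 2 and worse for someone who entered at RB 1. Adding (2,0,0), five of the ten fail the symptom limits RB = 0 and SF ≤ 1. These are counts of score combinations, not proportions of participants.

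**4. Which added condition closes the gap.** Adding RB = 0 leaves 6 of the 10 combinations. Adding RB = 0 and SF ≤ 1 leaves 5. Both exclude (1,1,0). Requiring only that no subscore exceeds 1 leaves 7 and still admits (1,1,0).

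**5. Size.** The documents do not give the share of participants entering at (1,1). As an assumption, take 5%, 10% or 20%. If all of them kept SF 1 and RB 1 and were rated PGA 0, the PGA-only route would contribute at most:

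- Cohort 1: 0.05 × 150 = 7.5, 0.10 × 150 = 15, 0.20 × 150 = 30 participants.
- Cohort 2: 0.05 × 100 = 5, 0.10 × 100 = 10, 0.20 × 100 = 20 participants.

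That is at most 5, 10 or 20 percentage points. The route in step 3 through SF 0 with bleeding is separate, and the documents give no basis for sizing it.

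**6. Other places a condition could sit.** Section 10.4.4 refers to Table 10.4.3-1 for all secondary endpoints, but the partial Mayo endpoints are not in that table. The treatment failure rules in Section 7.7.2.1 cover medication changes, colectomy or ostomy, and stopping for lack of effect. They do not cover symptom scores.

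**The case against.** **The effect is narrow.** This stands. Eight of the nine eligible SF/RB pairs need symptom improvement, and even at (1,1) the physician must rate PGA 0 while bleeding continues. The documents do not prevent that rating, but nothing in them suggests it would be common. A reader might infer that long-term remission as a whole is driven by the physician's rating, or that 4 of 10 combinations means about 40% of remitters are bleeding. Neither follows.

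**The cut-off of 2.5 suggests averaged diary scores.** This stands in part. With integers, 2.5 is no different from 2, and RB and SF are recorded over 7 days before visits. No averaging rule is given, however. Under averaging the counts of 10, 4 and 5 would not apply, but (1,1,0) would still qualify, and so would any SF + RB up to 2.5 with PGA 0.

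**The instruments are labelled separately and no comparison across visits is planned.** This is true of the readable text. A reader might infer that a stable or rising remission rate from Week 12 or 26 to Week 52 or 104 would be an artefact of the looser rule. The documents do not establish that. They show only that the two rates would not be comparable as defined.

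**A condition may appear in the SAP.** Section 10.4.4 leaves detail on secondary endpoints to the SAP, Appendix 6 lists selected definitions, and some text is redacted. The supplied document contains no such condition, so this remains open.

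**Replacing the rule would create a hybrid endpoint.** This stands as an argument against redefinition. Section 10.4 sends major changes to key endpoint definitions through a protocol amendment, and the score-only rate can reasonably be kept.

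**Conclusion.** The point holds in a limited form. As written, the rule counts as remission a participant who entered at SF 1 and RB 1 and has not changed, provided PGA is rated 0. It is met before treatment if PGA was 0 at baseline. It also admits participants with continuing bleeding whose SF has fallen to 0. Both outcomes fail the symptom part of the protocol's modified Mayo remission.

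The arithmetic is certain for the (1,1) case whether or not subscores are averaged. The effect on the reported rate is unknown: the ceiling of 5 to 20 points rests on an assumed 5% to 20% of participants entering at (1,1), with every one of them taking the PGA-only route. The documents do not support a claim of general upward bias across the cohorts from this rule. It concerns a descriptive secondary endpoint and its corticosteroid-free version. It is worth correcting because the correction is cheap, and because without it continuing bleeding could be read as durable remission.

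**What to change.** Keep the score-only rate as defined in Appendix 6, and prespecify the following in the SAP before database lock:

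1. For remission and corticosteroid-free remission at Weeks 52 and 104, show beside the score-only rate the rate that also requires RB = 0 and SF ≤ 1 with at least a 1-point decrease from baseline.
2. Report, by cohort, the number of participants whose baseline partial Mayo score is already ≤ 2.5.
3. Report the same partial Mayo rule at Week 12 for Cohort 1 and Week 26 for Cohort 2, so that any statement about durability uses one definition.

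No new data are needed. Tables 2-1 and 2-2 already collect SF, RB and PGA at Day 1 and at Weeks 12, 26, 52 and 104. The existing definition is untouched, so this should not by itself call for the amendment that redefinition might.

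The cost is a little more analysis and a symptom-conditioned rate that can only be equal to or lower than the score-only rate. Someone who enters at SF 1 must reach SF 0 to count, as under the modified Mayo rule. SF and RB are reported by unblinded participants, so open-label bias in them remains. SF 0, RB 0, PGA 2 would still qualify.
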